**Table L-2: Data Collection Schedule**

DATA	Screening / Baseline	Index Procedure	Hospital Discharge	1-Mo. F/U (±15 days)	12-Mo. F/U (±60 days)	24, 36, 48 & 60-Mo. F/U (±60 days)
GENERAL						
Informed Consent	✓					
Inclusion Criteria/ Exclusion Criteria	✓					
Physical Examination	✓			✓	✓	✓
Medical History	✓					
Current Health Status and Risk Factors	✓					
Device and Procedure Information		✓				
Pre-implant Adjunctive Procedures		✓				
Hospital Discharge Information			✓			
Adverse event assessment	✓ a	✓	✓	✓	✓	✓
EQ-5D questionnaire	✓			✓	✓	✓
IMAGING						
CT/MRI with contrast b	✓ f			✓ c,d,f	✓ d,f	✓ d,g
Angiography		✓ e				

a In case of screen failures, investigators are requested to enter safety information in the eCRF from time point of enrolment until time point of screen failure

b CT evaluation may include “3-phase technique”, volume studies, 3-D reconstruction, or computer-aided measurements

c A CT/MRI with contrast acquired at discharge (or before Day 15) due to medical necessity may be used to meet the 1-month follow-up visit CT/MRI requirement if a CT/MRI with contrast cannot be obtained within the 1-month follow-up window due to the subject’s health status based upon physician discretion.

d MRI with contrast may be used for those patients experiencing renal failure or who are otherwise unable to undergo contrast-enhanced CT scan, with TEE being an additional option in the event of suboptimal MR imaging.

e Required to complete Procedure eCRF but not expected to be submitted to Medtronic or core lab unless further analysis is needed.

f Imaging assessed by core lab

 Upon sponsor request, core lab analysis of imaging may be required

**M VERSION HISTORY**

Version	Summary of Changes	Author(s)/Title
1	
 
• Not Applicable, New Document
 
	
2	
 
• Minor typo changes
 
• Changes made in                             
 
○ Geographies
 
○ Principal Investigator
 
 
 
• Exclusion of vulnerable populations
 
• Protocol made compliant to ISO14155
 
• Updated to clarify imaging requirements
 
• Correction of the process of source data collection
 
• Insertion of missing safety and compliance definitions and/or references to study plans
 
	
3	
 
• Added Appendix L to reflect Protocol amendment to extend the follow of subjects from 12 months to 60 months.
 
• Administrative changes like correction of typo's, font types and alignments, integration of new template,
 
• Synopsis update with schedule of events and secondary endpoints for extended follow-up
 

SAE	Serious Adverse Event
SAS	Statistical Analysis System
SOC	System Organ Class
US	The United States

3. Introduction

This document outlines the detailed statistical methods to be implemented for the data collected within the scope of Valiant Evo US Clinical Trial and in conjunction with data collected during the concurrently enrolling Valiant Evo International Clinical Trial. This document is designed for internal use as a guideline for study Biostatistician and Statistical Programmer(s). Study protocol of the Valiant Evo US Clinical Trial is the primary resource if clarification is needed for the contents of this document. Analysis results obtained from the analyses outlined in this document will be the basis of the Clinical Study Report for this study.

As with any statistical analysis plan, the proposed methods and approaches to the data analysis should be viewed as flexible. Changes to the plan may arise if the emerging picture suggests that deviations from the original plan would provide a more reliable and valid analysis of the data. The purpose of this plan is to provide general, and in some instances, specific guidelines from which the analysis will proceed. Nonetheless, sound statistical reasoning must substantiate deviations from these guidelines.

4. Study Objectives

The purpose of the Valiant Evo US Clinical Trial is to demonstrate the safety and effectiveness of the Valiant

Evo Thoracic Stent Graft System in subjects with a descending thoracic aortic aneurysm (DTAA) who are candidates for endovascular repair.

The clinical evidence collected as part of this trial will be used in conjunction with data collected during the concurrently enrolling Valiant Evo International Clinical Trial to support PMA Approval of the Valiant Evo Thoracic Stent Graft System.

5. Investigation Plan

The Valiant Evo US Clinical Trial is a prospective, multi-center, pre-market, non-randomized, single-arm trial.

Subject population will include subjects diagnosed with DTAA who are considered candidates for endovascular repair, and who meet the Inclusion/Exclusion Criteria for the Valiant Evo US Clinical Trial. Inclusion and exclusion criteria are defined in the Clinical Investigation Plan Section D.

At enrollment, those subjects who sign and date the informed consent document, meet all of the study eligibility criteria, and are approved by the IPR will be eligible for inclusion into the Valiant Evo US Clinical Trial. The subject will only be considered enrolled when arterial access is established and an attempt to introduce the Valiant Evo Thoracic Stent Graft is made. A single, primary stent graft may be used by itself if its size is sufficient to provide the desired coverage. Alternatively, it may be used in combination with additional stent graft sections that increases the graft length distally or proximally to the primary section.

The Valiant Evo Global Clinical program will be conducted under both the Valiant Evo US Clinical Trial protocol and Valiant Evo International Clinical Trial protocol, and will enroll up to 37 sites worldwide. Inclusion will be halted at sites that reach the 20% inclusion cap. There will be no minimum number of subjects for a single investigational site. Globally, a total of 100 subjects will be concurrently enrolled in the United States and outside the United States to support the primary endpoints. Up to 50% of subject data used to support PMA approval may come from subjects enrolled at sites outside of the US under the Valiant Evo International Clinical Trial protocol.

The primary endpoint analysis will be completed upon 87 evaluable subjects reaching the 30 day endpoint. The data obtained from these 87 evaluable subjects will be used to support PMA-s Approval of the Valiant Evo Thoracic Stent Graft System and to support any other future Medtronic submissions to regulatory bodies.

Subjects enrolled under the Valiant Evo US Clinical Trial require follow-up evaluations at the following time points:

- 1 month following the index procedure (30 ± 15 days)
- 6 months following the index procedure (183 ± 30 days)
- 12 months following the index procedure (365 ±60 days)
- 24 months following the index procedure (730 ±60 days)
- 36 months following the index procedure (1095 ±60 days)

- 48 months following the index procedure (1460 ±60 days)
- 60 months following the index procedure (1825 ±60 days)

Note that the 6-month follow up is not mandatory for subjects enrolled under the Valiant Evo International Clinical Trial protocol. Available 6-month follow-up data from the international trial will be used for analysis.

Subjects will be followed until the last subject enrolled has completed the 1 year follow-up visit or until PMA approval is obtained in the US (whatever is later), however, Medtronic will work with FDA to determine if longer term follow after PMA approval is required. A post-approval analysis of 1-year Major Device Event (MDE) rate is planned.

6. Determination of Sample Size

One hundred (100) enrolled subjects will ensure 87 evaluable subjects at 30 days. The primary endpoint analysis will be completed upon 87 evaluable subjects reaching the 30 day endpoint. Based on Valor II study results, Valiant Evo is expected to perform similarly and have 6% of MDE combined with access and/or deployment failures at 30 days. The sample size of 87 evaluable subjects will provide 85% statistical power for the study hypothesis. The type I error is controlled at the one-sided 0.025 level.

Table 1: Power Analysis

True rate of MDEs combined with access and/or deployment failures at 30 day with Valiant Evo	6%
Performance Goal	16%
Significance level	0.025
Statistical test	One-sided binomial test
Evaluable sample size	n=87
Enrollment	Minimum of 100 subjects enrolled to ensure 87 evaluable subjects
Statistical power from the 87 evaluable subjects	85%

One hundred (100) enrolled subjects will also ensure 63 evaluable subjects at 1-year on MDE rate for the post-approval analysis. The VALOR II study with the Valiant stent graft system enrolled 160 patients with DTAA and was assessed through 12 months for purposes of PMA (P100040) approval. Through 1-year post-

treatment, the rate of MDEs combined with access and/or deployment failures was 7.1% (11/153) (Medtronic internal data using the Valiant Evo proposed definition). Therefore, for the purpose of post approval analysis, the rate of MDEs combined with access and deployment failures at 1-year with Valiant Evo is estimated to be 7.1% (refer to Table 22 below for power analysis assumptions).

Table 2: Power Analysis for Post-approval Analysis of 1-year Endpoint

Estimated rate of MDEs combined with access and/or deployment failures at 1 year with Valiant Evo	7.1%
Performance Goal (PG) at 1-year	20%
Significance level	0.05
Statistical test	One-sided binomial test
Evaluable sample size	N = 63 at 1 year
Enrollment	IDE cohort will enroll a minimum of 100 subjects and is expected to have a minimum of 63 evaluable subjects at 1-year follow up.
Statistical power from 63 or more evaluable subjects	92% (overall study power for passing both hypotheses is 81%)

7. Statistical Methods

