### F.2.4 Follow-Up Visits and Procedures

Each subject will have required post-implantation follow-up visits at 30 days and 12 months. Follow-up visits and associated timeframe windows are summarized in Table F-1.

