### F.3 Data collection requirements

Clinical data will be collected preoperatively to establish eligibility, at baseline, during the index procedure, throughout the hospital stay, and postoperatively at the required follow-up visits described in Section F.2. The data collection schedule is summarized in Table F-2. Imaging for baseline and follow-up assessments, as specified in Table F.2, will be sent to a Core Lab for analysis. In addition, any interim imaging of the stent graft region done within one year of implantation should be recorded on the interim image eCRF (e.g. 6-month imaging follow-up when performed as standard of care and/or when performed further to any issue observed at previous imaging follow-up). In case further analysis is needed, procedural and interim imaging exams are to be submitted to Core Lab.

Study data will be collected using electronic case report forms (eCRFs) as will be described in Section G.1. eCRFs should be electronically reviewed and approved by the clinical investigators. Medtronic monitors will perform source document verification of the eCRFs. The monitoring strategy will be defined in the monitoring plan.

For test equipment critical for assessing endpoints (e.g., CT scan, MRI, Transesophageal echography (TEE)) maintenance and calibrations will be monitored periodically.

It is expected that the Investigator enrolling the subject at the participating site where the implantation occurred will follow the subject during the course of the study. It is the responsibility of the Investigator to make sure that the subject is followed and that integrity and accuracy of the data is maintained.

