- Aneurysm-Related Mortality within 365 days
- MDEs within 365 days
- All AEs within 365 days including:
 - MAEs
 - SAEs
- Secondary procedures within 365 days
- Loss of stent graft patency within 12 months based on imaging findings
- Endoleaks at 12 months based on imaging findings
- Stent graft migration at 12 months as compared to 1-month imaging
- Aneurysm expansion > 5mm at 12 months based on imaging findings relative to the 1-month visit

Secondary endpoints are to be assessed beyond 12 months. The following secondary endpoints are to be evaluated at 24, 36, 48, and 60 months:

- All-cause mortality
- Aneurysm-Related Mortality
- MDEs
- All AEs and SAEs
- Secondary procedures
- Loss of stent graft patency based on site reported imaging findings
- Endoleaks based on site reported imaging findings

- Stent graft migration as compared to 1-month imaging
- Aneurysm expansion > 5mm based on site reported imaging findings relative to the 1-month visit

Health-related quality of life outcomes are to be assessed at all scheduled follow-up visits using the EQ-5D questionnaire.

Stent graft migration will be determined by the core lab or site imaging case report from (CRF). Core lab assessment and site reported result will be analyzed separately. Aneurysm expansion will be calculated. When 1-month image is not available, the latest image taken prior to 1-month will be used for calculation.

Descriptive statistical analyses will be performed on secondary endpoints. No inferential statistical analysis is planned for secondary endpoints.

Non-image endpoints event rates such as mortality, secondary procedures, MAEs, SAEs, conversion to open surgery, and thoracic aortic aneurysm ruptures through 1 year will be calculated in the same way as the MDE rate, specified in Table 5. The event rates beyond 1 year through 5 years will be analyzed using Kaplan Meier method.

Imaging based Event Rate Calculation:

Unless otherwise specified, imaging assessment will be performed by site as well as the core lab. Assessments from the core lab will be the primary result for the PMA and PMA-s submissions and analyzed separately from those by site. Imaging based event rate will be calculated using statistical analysis windows as follows (Table 6):

Table 6: Imaging based Event Rate Calculation:

Event rate = m/n	At 1 Month	At 6 Months	At 12 Months

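### Pooled 6-month imaging rates mix a required US evaluation with unscheduled International scans, so the denominator can depend on the finding and the rates may read too high

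*SAP*

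**What the plan says.** **Schedule.** SAP section 5 lists a 6-month evaluation among those required of US subjects. It continues: "Note that the 6-month follow up is not mandatory for subjects enrolled under the Valiant Evo International Clinical Trial protocol", and then "Available 6-month follow-up data from the international trial will be used for analysis". Protocol F.2.4 agrees: "Each subject will have required post-implantation follow-up visits at 30 days and 12 months". Table L-1 of the follow-up extension adds annual visits from month 24 but nothing between months 1 and 12.

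**Why an International scan exists.** SAP Table 3 sets the 6-month imaging window at Day 91-304, so any International scan in it is interim imaging. Protocol F.3 gives as examples a 6-month scan "when performed as standard of care and/or when performed further to any issue observed at previous imaging follow-up".

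**Who reads it.** Protocol F.3 says: "In case further analysis is needed, procedural and interim imaging exams are to be submitted to Core Lab". Protocol L.3.5.2 sends imaging up to the 12-month visit to the core lab and states no such condition, while Table L-2 marks core-lab reading only at baseline, 1 month and 12 months. SAP 7.9 says: "Assessments from the core lab will be the primary result for the PMA and PMA-s submissions". Site readings are analysed separately.

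**How the rate is formed.** In SAP Table 6 the At 6 Months rate is subjects with an event on a scan in the window, divided by subjects with a readable image in the window. SAP 7.4 does not impute missing images. SAP 7.3 assumes poolability and reviews it at analysis for the primary endpoint only.

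**The concern.** A rate with an available-image denominator describes the cohort only if having an image is unrelated to the finding. For US subjects the 6-month evaluation is scheduled. For International subjects two selection steps can each depend on the outcome:

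1. **Scanning.** A subject with an endoleak at 1 month is more likely to be scanned again, and more likely to show an endoleak at 6 months.
2. **Submission.** Under F.3, the core lab sees an interim scan when someone judges that it needs further analysis, and the core-lab reading is the primary imaging result.

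Subjects without a problem are the ones most likely to leave the denominator. SAP 7.3 bases poolability on similar eligibility, treatment, event definitions and oversight. Follow-up schedule is not on that list, and it is where the trials differ at 6 months. The SAP specifies no split by trial and no sensitivity analysis for 6-month imaging; the optional tipping-point analysis in 7.4 is for the primary endpoint. At stake is the accuracy of descriptive 6-month rates in a US submission in which up to half of the subject data may come from outside the US.

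**Working it through.** The documents state no 6-month imaging rate, scan-completion rate or precision target, so there is no plan figure to reproduce. The check is how far selection could move the Table 6 rate.

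**Inputs from the documents**
- 100 subjects in all (SAP section 5) and 47 International (Protocol C.7).
- US subjects taken as 100 - 47 = 53. This split is an assumption. SAP section 5 allows up to 50% from outside the US.

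**Inputs assumed**
- p: true 6-month prevalence of the finding, equal in both trials.
- sE and sN: probability that an International subject with (sE) or without (sN) the finding has a readable scan that enters the analysis.
- US scanning complete.

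**Formula**

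Expected pooled rate = (53p + 47p·sE) / (53 + 47p·sE + 47(1 - p)·sN)

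Worked case, p = 15%, sE = 0.8, sN = 0.2:
- Numerator: 53 × 0.15 + 47 × 0.15 × 0.8 = 7.95 + 5.64 = 13.59
- Denominator: 53 + 5.64 + 47 × 0.85 × 0.2 = 53 + 5.64 + 7.99 = 66.63
- Pooled rate: 13.59 / 66.63 = 20.4%
- International rate alone: 5.64 / (5.64 + 7.99) = 41%

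| p | sE / sN | Pooled rate | Bias (points) |
|---|---|---|---|
| 15% | 0.5 / 0.5 | 15.0% | 0 |
| 15% | 0.8 / 0.4 | 18.2% | +3.2 |
| 15% | 0.8 / 0.2 | 20.4% | +5.4 |
| 15% | 1 / 0 | 25.0% | +10.0 |
| 10% | any equal pair | 10.0% | 0 |
| 10% | 0.6 / 0.3 | 11.9% | +1.9 |
| 10% | 0.9 / 0.3 | 13.6% | +3.6 |
| 10% | 0.9 / 0.1 | 15.5% | +5.5 |
| 10% | 1 / 0 | 17.3% | +7.3 |
| 10% | 0.3 / 0.5 | 8.9% | -1.1 |

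A 50/50 split changes little: at p = 10% and 0.9/0.3 the pooled rate is 14.0% instead of 13.6%.

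The bias is zero when sE = sN, upward when sE > sN and downward when sE < sN. The 1/0 rows are the limit in which only subjects with the finding enter.

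**The case against.** A reader might infer that the rates are certainly biased upward, or that International subjects enter mainly because a problem was suspected. The documents support neither. F.3 names standard-of-care imaging first, and the share of triggered scans is not given. If most scans are routine, sE and sN are close and the bias is small; the table also has a downward case. This stands, and the claim is therefore conditional.

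Further points against:

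- **The core-lab filter is uncertain.** L.3.5.2 can be read as sending every scan up to month 12 to the core lab. Table L-2 points the other way. The passages must be reconciled. Even if every scan is sent, selection on which scans exist remains.
- **A mandatory US scan is an inference.** The SAP requires an evaluation, and the US protocol is not among the documents. The inference is reasonable because the SAP sets 6-month imaging endpoints, but complete US scanning is an assumption.
- **Site readings avoid the submission step.** This is correct: for them only selection into scanning applies. The core-lab results, however, are the primary ones.
- **Migration and expansion are less exposed.** Both are measured against the 1-month scan, so no earlier scheduled scan can already have shown them. The illustration fits endoleak best.
- **A misleading US/International contrast is not a planned output.** The SAP presents and tests the two trials separately for the primary endpoint only.
- **Sampling error is larger.** In the 0.8/0.2 case the 5.4-point shift is below the approximate 95% half-width, 1.96 × √(0.15 × 0.85 / 67) = 8.6 points. This is true, but an interval around the pooled rate does not account for selection.

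**Conclusion.** The point holds in a conditional form. Under the stated rules, the pooled At 6 Months denominator can depend on the outcome for International subjects. The pooled rates, above all core-lab endoleak, are likely biased upward if triggered scans are over-represented, and unbiased only if scanning and submission are unrelated to findings.

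The size is unknown. About +2 to +10 points covers assumed selection from moderate (0.6/0.3 at 10% prevalence) to the limiting case (1/0 at 15%). It rests on the 53/47 split, complete US scanning and equal true prevalence in the two trials.

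The consequence is limited. SAP 7.9 plans only descriptive analysis of secondary endpoints, and the 30-day primary endpoint, its test and its power do not use these scans. The change is still worth making because it is cheap and the plan has no other safeguard.

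**What to change.** In SAP section 5, section 7.9 and Table 6:

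1. Report 6-month imaging rates separately by trial, each with number scanned over number at risk. Subjects in study for at least 91 days, the threshold already used in Table 5, would serve as number at risk.
2. Make the US-cohort rate the main 6-month figure.
3. Show International Day 91-304 scans separately, with the reason for the scan (routine or triggered) if it is recorded. The documents do not show that it is.
4. Give any pooled rate only as supplementary.
5. Reconcile Protocol F.3, L.3.5.2 and Table L-2 on whether interim scans before month 12 go to the core lab.

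**Cost.** SAP wording and a table filter; International scans stay in the report. The main denominator falls to at most about 53. If the SAP's evaluable fractions (87 of 100 at 30 days, 63 of 100 at 1 year) applied to the US cohort, it would be about 53 × 0.87 = 46 to 53 × 0.63 = 33. At an assumed 15% prevalence the approximate 95% half-width, 1.96 × √(0.15 × 0.85 / n), is 9.6 points for n = 53, 10.3 for n = 46 and 12.2 for n = 33, against 8.6 for the pooled n of about 67 in the worked case.

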k = No. of Subjects Who Had No MDE	No. of subjects who have been in study for at least 1 day and without an MDE.	No. of subjects who have been in study for at least 91 days and without an MDE.	No. of subjects who have been in study for at least 305 days and without an MDE.

If a subject is early terminated from the study, the last day that the subject has been seen will be the duration in study, which can be the day of last follow-up, last imaging taken, an AE reported, or withdrawal from the study. If a subject is still in the study, the duration in study will be the time from index procedure to the cut off day that the database is locked or data snapshot is taken.

Subgroup analyses by-sex, by-race (based on subjects enrolled in the US only, since collection of race and ethnicity data may not be allowed outside the US as per local law and regulation), FreeFlo versus Closed Web configuration as proximal component, percutaneous access versus non-percutaneous, and by-region/study site will be performed on the primary study endpoint using descriptive statistics and reviewed for

clinical significant difference.

Secondary Endpoints

30-day Secondary Endpoint

The following secondary endpoints will be evaluated within 30 days post treatment:

- Peri-operative mortality
- All adverse events (AE) within 30 days including:
 - Major Adverse Event(s) (MAE)
 - Serious Adverse Event(s) (SAE)
- Secondary procedures
- Loss of stent graft patency at 30 day visit based on imaging findings
- Endoleaks at 30 day visit based on imaging findings

Detailed definitions of MAEs are defined in the Clinical Investigational Plan Appendix L.2.2. MAEs will be identified using codes in the Medical Dictionary for Regulatory Activities (MedDRA) provided by the Medtronic Clinical Safety group.

6-month Secondary Endpoints:

The following secondary endpoints will be evaluated:

- All-cause mortality within 183 days
- Aneurysm-Related Mortality within 183 days
- MDEs within 183 days
- All AEs within 183 days including:
 - MAEs
 - SAEs
- Secondary procedures within 183 days
- Loss of stent graft patency within 6 months based on imaging findings
- Endoleaks at 6 months based on imaging findings

- Stent graft migration at 6 months as compared to 1-month imaging
- Aneurysm expansion > 5mm at 6 months based on imaging findings relative to the 1-month visit

12-month Secondary Endpoints

The following secondary endpoints will be evaluated:

- All-cause mortality within 365 days

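### The SAP does not say consistently which endpoint its powered 1-year post-approval test uses: it is named an MDE rate but planned on MDE combined with access/deployment failure

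*SAP*

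**What the plan says.** **Name of the analysis.** SAP 5 (Investigation Plan) states: "A post-approval analysis of 1-year Major Device Event (MDE) rate is planned". SAP 6 (Determination of Sample Size) says that 100 enrolled subjects "will also ensure 63 evaluable subjects at 1-year on MDE rate for the post-approval analysis".

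**Planning inputs.** The same SAP 6 takes its rate from VALOR II, 11/153 at 1 year, for MDE together with access or deployment failure. It concludes that "the rate of MDEs combined with access and deployment failures at 1-year with Valiant Evo is estimated to be 7.1"%. Table 2 puts that composite rate beside a 20% performance goal, significance level 0.05, a one-sided binomial test, 63 evaluable subjects and 92% power. It adds that "overall study power for passing both hypotheses is 81"%, so a second hypothesis test is clearly intended.

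**Calculation rules.** SAP 7.9 lists four MDE components: device-related secondary procedure, device-related death, conversion to open surgery and aneurysm rupture. Access and deployment failure form a separate arm of the primary endpoint. The rule that joins the two arms is written for 30 days only. For 365 days there is only Table 5, whose numerator is subjects with an MDE and whose event-free count is: "No. of subjects who have been in study for at least 305 days and without an MDE".

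**Hypotheses.** SAP 7.9 states H0 and Ha for the 30-day goal of 16% and none for 1 year. MDEs within 365 days appear among the secondary endpoints, for which the SAP says: "No inferential statistical analysis is planned for secondary endpoints". SAP 7.5 mentions the post-approval analysis only to say that it needs no multiplicity adjustment.

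**The concern.** A test with a numerical goal, an alpha level and a claimed power needs one defined endpoint. Here the name and the only 365-day formula point to MDE alone, while the planning rate and the power table point to the composite.

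A programmer who follows the name in SAP 5 and 6 and the rule in Table 5 would code MDE alone. Every subject with an MDE is also a composite failure, but not the reverse. The rate tested would then omit one component of the rate on which the test was planned, and the 92% and 81% power figures would describe a different endpoint.

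The data are open-label and no 1-year hypothesis is written down. The choice between the two readings could therefore be made after the results are known.

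**Working it through.** **1. Reproduce the plan's figures.** The exact one-sided rule passes if the event count X is at most c, where c is the largest value with P(X ≤ c | n, p0) ≤ alpha. Power is P(X ≤ c | n, p1), with X binomial.

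- 1 year (Table 2: n = 63, p0 = 0.20, p1 = 0.071, alpha = 0.05): P(X ≤ 7) = 0.0473 and P(X ≤ 8) = 0.0937 under p0, so c = 7. Power = P(X ≤ 7 | 63, 0.071) = 0.923, against 92% stated.
- 30 days (Table 1: n = 87, p0 = 0.16, p1 = 0.06, alpha = 0.025): c = 7, size 0.0233, power 0.849, against 85% stated.
- Joint power: independence gives 0.849 × 0.923 = 0.784. Nesting the 63 within the 87, with the composite at both times, gives 0.831. The stated 81% lies between these and does not settle which 1-year endpoint is meant.

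Table 2's power therefore reproduces on composite inputs. (11/153 is 7.19%; using it gives power 0.919, which is immaterial.)

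**2. What Table 5 does with an access or deployment failure that is not an MDE.** The subject is not in m. If in study for at least 305 days, the subject enters k as event-free; otherwise the subject leaves the denominator. The first route is open. Protocol F.2.2 follows treatment failures for 30 days and then per standard of care, but records their serious adverse events for the whole trial and completes the exit form at the end of the study. SAP 7.9 counts time in study up to the data cut-off for anyone still in it.

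**3. Direction.** Let the composite count be x of n, with one such subject.

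- Moved to k, the count is x − 1 of n, and P(X ≤ x − 1 | n) ≤ P(X ≤ x | n).
- Dropped, it is x − 1 of n − 1. Since P(X ≤ x | n) = P(X ≤ x − 1 | n − 1) + (1 − p)·P(X = x | n − 1), the p-value again cannot rise.

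Either way the test is as easy or easier, never harder.

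**4. One-subject example.** Take seven MDEs plus one access-only failure.

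- Composite: 8/63, p = 0.094, goal not met.
- MDE alone, subject in k: 7/63, p = 0.047, goal met.
- MDE alone, subject dropped: 7/62. P(X ≤ 6 | 62) = 0.0238, and 0.0473 = 0.0238 + 0.8 × P(X = 7 | 62) gives P(X = 7 | 62) = 0.0294. So p = 0.0238 + 0.0294 = 0.053, goal not met.

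In this example the conclusion reverses only when the subject has reached 305 days.

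**5. Size over an assumed range.** The documents do not split the 11/153. *Assumption:* failures without an MDE supply d percentage points of the composite rate, and all those subjects stay in the denominator, so n = 63 and c = 7.

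| d (points) | Pass probability, true composite 20% (MDE rate 20% − d) | Power, true composite 7.1% (MDE rate 7.1% − d) |
|---|---|---|
| 0 | 4.7% | 92.3% |
| 1 | 6.9% | 96.3% |
| 2 | 9.9% | 98.6% |
| 3 | 13.9% | 99.6% |
| 4 | 19.0% | 99.9% |

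**The case against.** The strongest reply is that the composite is plainly meant and MDE is shorthand. Table 2 is the only place that holds goal, alpha and test, and its only endpoint row is the composite. SAP 6 ties the composite rate expressly to the post-approval analysis. The International protocol uses the same shorthand: the note to Table C-1 calls the 5.6% composite rate an MDE rate, and H.1 describes the composite primary endpoint as the proportion with an MDE. This has force, and it limits what can be claimed.

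- A reader might infer that the SAP does test the easier endpoint. The documents do not show that. Table 5 is never linked to the powered test, and its 30-day column is also MDE-only although the 30-day test is explicitly composite. What is missing is the 1-year sentence that adds access and deployment failures.
- A reader might infer that the bar on inference for secondary endpoints contradicts the powered test. It does so only if that test is MDE-only. A composite test and a descriptive MDE rate can coexist.
- A reader might infer that an access failure always becomes a 1-year success. That needs at least 305 days in study.
- A reader might take the pass probabilities as an established error rate. The value of d is assumed, and it is zero if every access or deployment failure is also an MDE, for example through conversion to open surgery.
- That the 20% goal belongs to the composite is inferred from its place in Table 2. No derivation is given.

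SAP 3 also names the US trial protocol as the primary resource for clarification. It was not available, and it may define the 1-year endpoint.

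What survives is the conflict inside the SAP. Shorthand explains the label, but it supplies neither a 365-day composite rule nor a 1-year hypothesis.

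**Conclusion.** The point holds as an inconsistency. The powered 1-year test has two possible endpoints, no stated hypothesis in SAP 7.9, and a composite calculation rule only at 30 days. If it is run as named and under Table 5, subjects with an access or deployment failure and no MDE are never failures, and the test is equal to or easier than the one planned.

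The documents do not fix the size. Over the assumed 0 to 4 points, the chance of passing at a true composite rate of 20% runs from 4.7%, which is no effect, to 19.0%. This takes the 20% goal as a composite goal and keeps all 63 subjects in the denominator.

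The correction should be made before the 1-year analysis, but it ranks below an essential change. The analysis is post-approval, and neither the 30-day primary test nor the International protocol's descriptive 30-day interval depends on it.

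**What to change.** In SAP 7.9:

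1. Define the 1-year endpoint as access or deployment failure, or an MDE with onset from Day 0 to Day 365.
2. Count access and deployment failures as failures whatever the follow-up time. Apply the 305-day requirement only to subjects counted as event-free on the composite.
3. State H0: p ≥ 20% against Ha: p < 20%, exact binomial, one-sided 0.05.
4. Keep the 365-day MDE-only rate as a descriptive secondary endpoint, and say that the post-approval composite test is separate from the secondary endpoints.

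In SAP 5 and 6, replace the MDE label for this analysis with the composite.

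The cost is SAP wording and one extra term in the 1-year derivation. The sample size of 63, the cut-off of 7 events and the stated power do not change. The reported 1-year rate may be slightly less favourable.

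If the sponsor intends MDE alone, the planning rate, goal and power should be re-derived for MDE alone. The sponsor would need the split of the VALOR II 11/153, which it describes as internal data. The 1-year test would then also need an explicit exception from the bar on inference for secondary endpoints.
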